Patients eligible to receive TeleGRACE services include:

- Veterans discharged from the Indianapolis VA medical center (VAMC) for an medical/surgical diagnosis (excludes substance use disorder-related admissions; excludes planned admissions)
- Age ≥ 70 years
- Not enrolled in home-based primary care (HBPC)
- Not enrolled in hospice
- Not in dialysis
- Primary care visit within VA in the prior 2 years
- Not residing in nursing home, skilled nursing facility, or CLC
- CAN score $\geq 95^{\text{th}}$ percentile for mortality or missing CAN score
- Discharged from the hospital alive

Exclusion Criteria

- Patients who have been randomized to the control arm after their index hospitalization who become readmitted to the hospital may not be re-randomized.
- Enrolled in in-person GRACE
- Enrolled in home-based primary care (HBPC)
- Enrolled in hospice
- Enrolled in complex care program
- Dialysis (hemodialysis or peritoneal dialysis)
- Residing in nursing home, skilled nursing facility, or CLC
- Living >60 miles from the Indianapolis VAMC facility

Outcome Measures

The primary outcome for the TeleGRACE evaluation will be:

- 90-day all-cause mortality (measured as 90-days from discharge from the index hospital stay)

The secondary outcomes are:

- 90-day readmissions
- 1-year all-cause readmissions
- 1-year mortality
- 1-year ED utilization (VA and non-VA)
- 1-year falls

We will explore using time to nursing home placement as a secondary outcome. We have requested the data and will evaluate the data source for completeness; comparing it against chart review. If the team considers the data source to be accurate, then we will examine time to nursing home placement as a secondary analysis.

Randomization

Patients will be randomized in ratio of 1 (control):2 (intervention) stratified by site of primary care (Indianapolis VAMC versus non-Indianapolis [e.g., CBOCs]). We created a computer-generated randomization list (with random block sizes of 3 or 6) for each strata. With the current capacity

of VA GRACE program staff, our goal is to enroll 5 patients to TeleGRACE each month. The project will seek to enroll a total of 180 patients to TeleGRACE and 360 to usual care in a three-year recruitment period.

Data Sources

Corporate Data Warehouse (CDW) data

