CDW data will be used to assess patient baseline characteristics (e.g., age, demographics, past medical history, prior healthcare utilization) as well as outcomes (i.e., ED utilization, readmission, mortality, and falls). In this way, the same data source is used to identify outcomes for both intervention and control patients.

Chart Review data

Chart review will be used to validate the TeleGRACE dose classification that is based on CDW data (see Per-Protocol analysis described below).

Follow-up Period

Patients will be followed for one year from the date of discharge from their index hospitalization. Unlike clinical trials that require in-person outcome assessments and hence implement “windows” for data collection, this evaluation will use electronic health record data for outcome assessment and hence no windows will be specified.

ANALYSIS PLAN

Intention-to-Treat Analysis

We will compare baseline characteristics between TeleGRACE patients and control patients using chi-square tests for categorical data and t-tests for continuous characteristics.

In the primary intention-to-treat (ITT) analysis, we will compare outcomes between patients randomized to usual care and those to TeleGRACE adjusting for the baseline characteristics that are significantly different by logistic regression for the binary outcome and Poisson regression for count data. If the sample size is sufficient, we will examine the effect of the TeleGRACE program by site of receipt of primary care services.

Per-Protocol Analyses

Not all patients who are randomized to receive TeleGRACE will receive services from the TeleGRACE staff. This situation is anticipated for patients who decline GRACE and others who become ineligible after discharge from the index hospitalization but before their first virtual home visit post-discharge (e.g., patients who die, get readmitted, or move to a skilled nursing facility after discharge). In the exceptionally rare case, patients may be discharged from TeleGRACE due to safety concerns for our staff (e.g., sexually or physically aggressive behavior, unwillingness to cage animals, unwillingness to store firearms). The per-protocol analyses will be similar to the planned intention-to-treat analysis but will compare the outcomes between patients who received GRACE service versus patients in usual care.

Given the expected heterogeneity in the number of TeleGRACE visits, patients will be classified into four categories as follows:

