 - d. If there are more than 10% patients censored for the outcomes, we will conduct Cox-regression analysis for the hazard of death and risk-exposure adjusted Poisson regression for the number of readmissions and number of falls.

POWER

For **Aim 1** (effectiveness of TeleGRACE versus usual care), we expect to observe 2% and 8% 90-day all-cause mortality for the TeleGRACE and usual care patients, respectively. This projected effect size is conservative based on our propensity-score weighting analysis comparing GRACE patients with usual care patients. With 180 TeleGRACE and 360 usual care patients, the study has 0.96 power at detect the efficacy of TeleGRACE program with a one-sided normal test at a significance level 0.05. Considering a 10% drop-out, the analysis has 0.94 power to establish the TeleGRACE efficacy with the same effect size.

DATA MONITORING

Enrollment

We will closely monitor the randomization of TeleGRACE with the expected rate of 5 per month. We will plot the number of actual randomized patients and its expected number against the study time and update the figure on a monthly basis. Prior to the DSMB meeting, we will estimate the current randomization rate and project the final number of randomized patients by end of the fourth year with the current rate along with its 95% confidence interval based on the Poisson distribution. If the upper bound of the 95% interval is below the target number of 180. We will modify the enrollment strategy to ensure that we achieve the enrollment goal.

Interim Analysis

Since the observed effect size of in-person GRACE versus usual care is quite substantial with respect to 90-day all-cause mortality, we plan an interim analysis when a half of the enrolled patients can be evaluated for the primary outcome. One-sided normal testing will be applied for the interim analysis using O'Brien-Fleming group sequential test with the overall type error controlled at 0.05. The hypotheses are:

$$H_0: p_1 = p_2 \text{ vs. } H_1: p_1 < p_2,$$

where p_1 and p_2 stand for the 90-day all-cause mortality in TeleGRACE and usual care arms, respectively.

If the Z – test statistic crosses the boundary of -2.54 at the interim analysis, the trial will be recommended for stopping for efficacy; otherwise, the trial will continue to the end with the crossing boundary for the test statistic at -1.66. The overall power with the interim analysis for this study is 0.82.

Safety

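### The primary ITT covariates are chosen by baseline significance tests that omit the stratification factor, and the Z behind the -2.54 and -1.66 boundaries has no stated variance form

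*Combined protocol and SAP*

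**What the plan says.** Under Analysis Plan, Intention-to-Treat Analysis, the plan first tests the baseline table: "We will compare baseline characteristics between TeleGRACE patients and control patients using chi-square tests for categorical data and t-tests for continuous characteristics". Then: "In the primary intention-to-treat (ITT) analysis, we will compare outcomes between patients randomized to usual care and those to TeleGRACE". The method given for that comparison is "adjusting for the baseline characteristics that are significantly different by logistic regression for the binary outcome". It gives no significance threshold and no covariate list. Randomization is "stratified by site of primary care (Indianapolis VAMC versus non-Indianapolis", but in the analysis site appears only as a by-site look if numbers allow, not as a model term.

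The Power section states that "the study has 0.96 power at detect the efficacy of TeleGRACE program with a one-sided normal test at a significance level 0.05", for 180 TeleGRACE and 360 usual care patients with mortality of 2% and 8%, and 0.94 after 10% drop-out. Interim Analysis sets one-sided hypotheses on p1 and p2 and an O'Brien-Fleming design with one look at half the patients. If the Z "crosses the boundary of -2.54 at the interim analysis, the trial will be recommended for stopping for efficacy"; otherwise the final boundary is -1.66. Overall power with the interim is given as 0.82. No variance form is stated, and nothing links this Z to the logistic analysis called primary.

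The Randomization section also contains two allocations that point in opposite directions: "Patients will be randomized in ratio of 1 (control):2 (intervention" and "The project will seek to enroll a total of 180 patients to TeleGRACE and 360 to usual care".

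**The concern.** Two parts of the primary analysis are left open.

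The first is the model. Under randomization, baseline differences between arms arise by chance. A rule that adjusts only for significant ones therefore picks covariates by accident rather than by prognostic value, and nobody can write the primary model down before seeing the baseline data. Stratified blocks of 3 or 6 hold site nearly balanced, so the one factor that the design singles out is the one that the rule will not select.

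The second is the decision statistic. Few deaths are expected at the interim, and with unequal arms the pooled and unpooled variances differ materially. If the form is not fixed, the same interim data can support opposite stopping recommendations, and the actual error rate of the -2.54/-1.66 rule is not known to be 0.05.

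**Working it through.** **Inputs from the plan.** Mortality 2% and 8%; 180/360 (TeleGRACE/usual care), or 162/324 after 10% drop-out; one-sided 0.05; one look at half the patients; boundaries -2.54 and -1.66. Because the stated ratio runs the other way, 360/180 is also computed.

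**Boundaries.** O'Brien-Fleming-type spending at half information spends 2[1 - Φ(1.96/√0.5)] = 0.0056 at the interim. This gives 2.538 and then 1.662, with overall error 0.0502 for the rounded values. The stated boundaries reproduce.

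**Fixed-design power.** Unpooled: SE = √(0.02×0.98/180 + 0.08×0.92/360) = 0.0177, and Φ(0.06/0.0177 - 1.645) = 0.959. At 162/324 the result is 0.942. Both match the stated 0.96 and 0.94. At the same sizes, a pooled null variance gives 0.915 and 0.885, arcsine 0.937 and 0.914, and a log-odds-ratio formula 0.819 and 0.783.

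**Two-look power.** With drift θ = 0.06/0.0177 = 3.39, power is 1 - P(Z₁ > -2.54 and Z₂ > -1.66), where the means are -θ√0.5 and -θ and the correlation is √0.5. This gives 0.959. So the formula that matches 0.96 does not lead to 0.82.

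**Exact two-look results.** These come from binomial enumeration of the interim (90/180 or 180/90), convolved with the second half.

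| TeleGRACE/usual care | Variance | Interim crossing, 2% vs 8% | Overall power | Null error at 8% | Null error at 5% |
|---|---|---|---|---|---|
| 180/360 | unpooled | 0.483 | 0.952 | 0.066 | 0.072 |
| 180/360 | pooled | 0.209 | 0.930 | 0.046 | 0.045 |
| 360/180 | unpooled | 0.204 | 0.914 | 0.040 | 0.039 |
| 360/180 | pooled | 0.406 | 0.943 | 0.053 | 0.056 |

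The interim recommendations differ in 0.483 - 0.209 = 27% of trials at 180/360 and 0.406 - 0.204 = 20% at 360/180. Conclusions over both looks differ in 2.2% and 2.9%.

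**Two illustrations.** At 90/180, take 1 versus 14 deaths (1.8 and 14.4 expected). The difference is 1/90 - 14/180 = -0.0667. The unpooled SE is 0.0228, so Z = -2.92 and crosses. The pooled rate is 15/270, the SE is 0.0296, and Z = -2.25 does not cross. At 180/90, take 3 versus 8 deaths (3.6 and 7.2 expected): unpooled Z = -2.29 does not cross and pooled Z = -2.83 does.

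**Covariate rule.** With K independent tests at an assumed 0.05, at least one covariate enters by chance with probability 1 - 0.95^K: 40% for K = 10, 54% for K = 15, 64% for K = 20. A simulation used 4,000 trials in each of 12 scenarios, 540 patients and stratified blocks of 3 or 6. It assumed 15 candidates of which one is prognostic, two equal sites with log-odds 0.3, and a single-look likelihood-ratio test at -1.66. Site was selected in 0 of 48,000 trials. Power is shown for unadjusted / rule / prespecified site plus the prognostic variable, at log-odds 0.4, 0.7 and 1.0 per SD:

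- 180/360: 0.943/0.941/0.944; 0.944/0.941/0.947; 0.942/0.942/0.948.
- 360/180: 0.935/0.931/0.935; 0.936/0.934/0.941; 0.932/0.933/0.948.

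From these rounded figures, prespecification gains 0.3 to 0.6 point at 180/360 and 0.4 to 1.5 points at 360/180 over the rule. Site alone adds nothing over the unadjusted test. Null rejection was 0.052-0.059 with the rule and 0.053-0.058 unadjusted at 180/360, and 0.042-0.047 and 0.041-0.049 at 360/180. A second simulation at 180/360, with 20 candidates of which three were prognostic at log-odds 0.8 per SD, gave 0.898 with the rule and 0.922 prespecified, a gap of 2.4 points.

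**The case against.** The hypotheses are written in p1 and p2 and tested by a one-sided normal test, so an unadjusted two-proportion Z is the natural reading of the boundary statistic. That stands. Contrasts with Wald or likelihood-ratio statistics from a logistic model rest on a less natural reading and carry little weight here. What stays open is pooled versus unpooled, and which result governs at the final look.

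The effect is mostly on timing. Nearly all trials with different interim recommendations reach the same conclusion, crossing leads only to a recommendation, and under the null at 8% the interim recommendations differ in only 1.0% (180/360) and 0.5% (360/180) of trials. That also stands. Each illustrative table is only one possible outcome.

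A reader might infer from the match with 0.96 and 0.94 that the plan uses an unpooled Z and therefore exceeds 0.05. The documents do not establish this. The figures are consistent with an unpooled Z at the stated 180/360, but a Z with pooled variance throughout at 360/180 and 324/162 gives 0.956 and 0.938, which round the same way. The excess error arises for the unpooled form at 180/360; at 360/180 that form is conservative.

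A reader might also infer from 0.82 that a second statistic was used, since a log-odds-ratio formula with both looks gives 0.817. The plan gives no source for 0.82, so this is only a numerical match.

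**Conclusion.** The point holds as two prespecification gaps that should be closed.

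The covariate rule makes the primary model data-dependent and in practice excludes the stratification factor. It is tempting to call this type I inflation, but the simulations show none relative to the unadjusted test. The power cost is about 1 point or less in most assumed scenarios and 2.4 points with three strong prognostic covariates. The plan gives no candidate list, threshold or prognostic strength, so these sizes rest on assumptions.

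The undefined variance form bears on a stated stopping rule. At 2% versus 8% it moves the chance of crossing at the interim between 0.209 and 0.483 at 180/360, and between 0.204 and 0.406 at 360/180, with the order of the two forms reversed. Null error at 8% mortality ranges from 0.046 to 0.066 and from 0.040 to 0.053. It would be too strong to say that the trial's conclusion depends on this choice. The omissions are certain from the text; the statistic intended by the plan remains an inference.

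**What to change.** (a) Delete the significance-based rule, report baseline data descriptively, and prespecify a short covariate set: site of primary care plus one or two expected prognostic variables already in the Corporate Data Warehouse, for example age or prior utilization.

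(b) First reconcile the 1:2 control-to-intervention ratio with 180 TeleGRACE and 360 usual care. Then name one statistic and its variance form for both boundaries. It must be defined when an arm has no deaths: at 2%, zero TeleGRACE deaths has probability 0.98^90 = 0.162 with 90 patients. Choose it by its exact null error at the reconciled sizes, since no candidate can be recommended before then. A site-stratified score test gives 0.045-0.047 at 180/360 but 0.053-0.057 at 360/180. A likelihood-ratio test gives 0.055-0.057 and 0.048-0.050. State that this statistic decides the primary hypothesis and that the prespecified logistic model supplies the adjusted estimate.

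(c) Restate fixed and two-look power for that statistic, and correct or explain 0.82.

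The cost is SAP wording and minor programming, with no new data collection. The stated power would fall slightly below 0.96: with both looks, the score test has about 0.93 at 180/360 and about 0.94 at 360/180.

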The Indianapolis VAMC GRACE program has been demonstrated to improve care and outcomes for older Veterans. In a propensity weighted data analysis with 634 GRACE patients and 5614 matched control patients, GRACE was significantly associated with lower all-cause mortality after discharge from an index hospitalization: all-cause mortality 90-day post discharge was 1.3% for GRACE patients and 8.5% for control patients. However, the reach of the program is limited due to logistical constraint of the 20-mile driving distance that the GRACE teams use for their home visits. **The overall objective of the TeleGRACE project is to improve the care and outcomes of older Veterans with a recent inpatient stay by expanding access to the GRACE program, by evaluating a telehealth implementation.** Specifically, the TeleGRACE project seeks to overcome the drive-time distance barrier that currently prevents the widespread application of GRACE to eligible older Veterans by implementing virtual home visits instead of in-person home visits.

The TeleGRACE evaluation will focus on three primary aims and a secondary aim:

Primary Aim 1: To examine the effectiveness of the TeleGRACE program, we designed a randomized controlled implementation trial (RCT) powered for the primary outcome of 90-day all-cause mortality. We will also examine its effectiveness for the secondary outcomes including 90-day readmissions, 1-year ED utilization (VA and non-VA), 1-year all-cause readmissions, 1-year mortality, as well as patient, caregiver, and staff satisfaction. We hypothesize that patients who receive TeleGRACE will have lower 90-day mortality than patients in usual care.

Primary Aim 2: to examine the implementation of the TeleGRACE program. The implementation strategy is reflecting & evaluating. Implementation outcomes are based on the REAIM framework and include reach, efficacy (Aim 1), and implementation (total number of Veterans served, fidelity).

Primary Aim 3: to conduct a business-case analysis (BCA). The business case analysis will calculate the net financial savings or loss for TeleGRACE as the difference in the overall intervention costs and savings due to downstream benefits for patients receiving TeleGRACE versus usual care controls.

TeleGRACE Program Evaluation

Activity	Year-1 (FY2021)				Year-2 (FY2022)				Year-3 (FY2023)				Year-4 (FY2024)				Year-5 (FY2025)			

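### The primary logistic regression names no test and no sparse-event method although only about 3.6 TeleGRACE deaths are expected, and the stated power of 0.96 belongs to a different test

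*Combined protocol and SAP*

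**What the plan says.** The primary outcome, in the Outcome Measures section, is "90-day all-cause mortality (measured as 90-days from discharge from the index hospital stay". The Intention-to-Treat Analysis section compares the randomized groups "by logistic regression for the binary outcome and Poisson regression for count data", with adjustment for any baseline variables found to differ significantly between the arms. It does not say whether the arm effect is tested by Wald, likelihood ratio or score, and it gives no fallback for an arm with no deaths or very few. The same section adds a conditional analysis by site: "If the sample size is sufficient, we will examine the effect of the TeleGRACE program by site of receipt of primary care services".

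The Power section states: "we expect to observe 2% and 8% 90-day all-cause mortality for the TeleGRACE and usual care patients, respectively". It continues: "With 180 TeleGRACE and 360 usual care patients, the study has 0.96 power", and describes the test as being "with a one-sided normal test at a significance level 0.05". With 10% drop-out the stated power is 0.94. The project rationale gives the background figures from in-person GRACE: "all-cause mortality 90-day post discharge was 1.3% for GRACE patients and 8.5% for control patients".

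The Interim Analysis section tests the same endpoint with a one-sided Z on the two mortality proportions (boundaries -2.54 and -1.66). The plan does not say how that Z relates to the adjusted logistic model.

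**The concern.** Ordinary logistic regression is fitted by maximum likelihood. When one arm has no events, the log odds ratio has no finite maximum, so software stops at an arbitrary large value with a huge standard error. Here the sparse arm is the one the plan hopes will do well, so the problem becomes more likely as the true benefit grows.

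Two things are at stake. The first is whether the primary analysis is certain to return a reportable effect estimate, with a test settled before the data are seen. If the estimator or test is chosen only after a zero or near-zero count appears, the primary result is open to challenge. The second is whether the stated power describes the analysis that the plan calls primary.

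**Working it through.** **Inputs.** Mortality of 2% and 8%, 180 TeleGRACE and 360 usual-care patients, one-sided 0.05 and 10% drop-out (162 and 324) come from the Power section. The rates of 1.3% and 8.5% come from the rationale. All calculations are unadjusted.

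**1. The plan's own figure.** Unpooled normal test of two proportions: power = Φ(|p1 − p2| / √(p1q1/n1 + p2q2/n2) − 1.645).
- 180/360: variance = 0.02 × 0.98/180 + 0.08 × 0.92/360 = 0.0001089 + 0.0002044 = 0.0003133. The square root is 0.01770, and 0.06/0.01770 = 3.390. Φ(3.390 − 1.645) = 0.959, matching 0.96.
- 162/324: 0.06/0.01866 = 3.216. Φ(3.216 − 1.645) = 0.942, matching 0.94.

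So 0.96 reproduces as the approximate power of this test. The pooled version of the formula gives 0.915.

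**2. Expected deaths.** TeleGRACE: 180 × 0.02 = 3.6 (162 × 0.02 = 3.2 after drop-out; 180 × 0.013 = 2.3 at the in-person rate). Usual care: 360 × 0.08 = 28.8, taken as 29 below.

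**3. Chance of no TeleGRACE deaths**, (1 − p)^n:
- 0.98^180 = 2.6%
- 0.98^162 = 3.8%
- 0.987^180 = 9.5%
- By site, if strata were equal (90 TeleGRACE patients each; the documents give no split): 0.98^90 = 16% and 0.987^90 = 31%.

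**4. Each statistic against 29/360 usual-care deaths** (z values; the one-sided critical value is -1.645):

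| TeleGRACE deaths (of 180) | Wald | Score (pooled Z) | Likelihood ratio (signed root) | Firth penalized LR |
|---|---|---|---|---|
| 0 | -0.001 | -3.91 | -4.93 | -4.56 |
| 1 | -2.70 | -3.59 | -4.20 | -3.99 |
| 2 | -2.79 | -3.27 | -3.70 | -3.54 |
| 3 | -2.68 | -2.96 | -3.27 | -3.14 |
| 4 | -2.49 | -2.67 | -2.89 | -2.77 |

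In the first row the ordinary fit stops at a log odds ratio of about -23 with a standard error of about 16,100. In this unadjusted two-by-two table the Firth estimate equals adding 0.5 to each cell: OR = (0.5 × 331.5)/(180.5 × 29.5) = 0.031, which is finite. A Wald test on that corrected estimate gives only z = -2.43, so the penalized likelihood-ratio test should be named along with the estimator.

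**5. Exact power**, by enumerating both binomials at one-sided 0.05 and counting a zero cell as non-significant for Wald:

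| | Wald | Score | Likelihood ratio | Firth penalized LR |
|---|---|---|---|---|
| 2% vs 8%, 180/360 | 0.897 | 0.933 | 0.940 | 0.929 |
| 2% vs 8%, 162/324 | 0.855 | 0.908 | 0.915 | 0.900 |
| Type I error, 8% in both arms, 180/360 | 0.044 | 0.048 | 0.054 | 0.046 |

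None of the logistic tests reaches 0.96 at 180/360 or 0.94 at 162/324.

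At 1.3% vs 8.5% and 180/360, Wald stays at 0.894 while Firth rises to 0.990. In a half-size stratum (90/180) at 2% vs 8%, Wald has 0.47 and Firth 0.69.

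**The case against.** A reader might infer that the most favourable result, no TeleGRACE deaths, would leave the primary analysis with a non-significant test. The documents do not support that. The failed p-value belongs to the Wald statistic, which the plan never names. On 0/180 vs 29/360 the likelihood-ratio test from the same logistic model gives chi-square 24.3 (p = 8 × 10⁻⁷), one-sided Fisher gives p = 5 × 10⁻⁶, and the pooled proportion Z of -3.91 is far past the final boundary of -1.66. That objection stands in full.

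Nor does the model break down at the expected counts. With 1 to 4 deaths against 29 it fits and Wald is significant. Given at least one TeleGRACE death, Wald power at 2% vs 8% is 0.921 against 0.931 for score, so most of the Wald loss comes from the zero cell, which has about a 1-in-40 chance at the planned rate. The 9.5% figure uses a rate from a propensity-weighted analysis of in-person GRACE. The plan assumes 2% instead, and its randomized arm will include patients who decline or never start. The by-site analysis is conditional and not primary. These points limit the size of the problem.

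Firth is also not the only remedy: naming a likelihood-ratio or score test would cure the test. It would not give a finite odds ratio when no TeleGRACE patient dies, because that failure comes from maximum likelihood whichever test is used. The plan's silence also leaves the choice of test open until the data are known.

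Finally, the counts rest on 180/360. The Randomization section also states a ratio of one control to two intervention patients, which contradicts it. With 360 TeleGRACE and 180 control patients, expected TeleGRACE deaths would be 7.2, the chance of none would be 0.98^360 = 0.07%, and Wald and likelihood ratio would both have power 0.938. The concern about sparse counts would then largely vanish.

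**Conclusion.** The concern holds in a limited form. The primary analysis lacks a named test and a sparse-event method while expecting 3 to 4 deaths in one arm. There is a small but real chance that it returns no finite odds ratio: 2.6% as planned, 3.8% after drop-out, and 9.5% at the in-person rate. The consequence for testing depends on a choice the plan has not made. At the planned rates the spread is from 0.90 (Wald) to 0.94 (likelihood ratio), a moderate difference.

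Separately, and whichever logistic test is chosen, 0.96 is not the power of the analysis called primary. It describes the unpooled normal test.

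These conclusions assume 180 TeleGRACE and 360 usual-care patients, no covariates and one-sided 0.05; the by-site figures also assume equal strata. This is a worthwhile, inexpensive improvement. It does not show that the trial would miss a true benefit.

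**What to change.** In the Intention-to-Treat Analysis section, specify Firth's penalized logistic regression for 90-day mortality and for any by-site version of it, with a penalized likelihood-ratio test and a profile-likelihood interval. Fix this before outcomes are seen.

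In the Power section, state the power of that analysis at 180/360: about 0.93, or about 0.90 with 10% drop-out. Reconcile the allocation ratio with the 180/360 targets first, since every figure here depends on it.

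The cost is about two sentences of wording and a standard software option. The stated power becomes slightly less favourable. Firth also gives up about one point of power against the ordinary likelihood-ratio test (0.93 vs 0.94), but that test's type I error is 0.054 against 0.046 for Firth.
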